8.3.3. Clinical Laboratory Abnormalities

Clinically significant abnormal laboratory findings or other abnormal assessments that are detected during the study or are present at baseline and significantly worsen following the start of the study

will be reported as AEs or SAEs. However, clinically significant abnormal laboratory findings or other abnormal assessments that are associated with a disease reported in the medical history, unless judged by the Investigator as more severe than expected for the subject's condition, or that are present or detected at the start of the study and do not worsen, will not be reported as AEs or SAEs.

The Investigator will exercise his or her medical and scientific judgement in deciding whether an abnormal laboratory finding or other abnormal assessment is clinically significant.

8.3.4. Recording of AEs and SAEs

During the study, site personnel will evaluate and record any change in the pre-existing condition(s) and/or the occurrence of any AEs.

Subjects will be questioned for the occurrence of any new or worsening sign or symptom at each study visit. The Investigator or designee will enquire about AEs by asking non-leading questions, such as in the following examples:

At the first scheduled AE enquiry on Day 0 (pre-dose) subjects will be asked:

“How are you feeling?”

At subsequent scheduled intervals subjects will be asked:

“Since you were last asked, have you felt unwell or different from usual?”

Out of range laboratory results arising once study treatment has begun, will be reviewed by the Investigator. The Investigator will determine whether the signs and symptoms represent clinically significant changes from the subject's baseline, and if so, they should be recorded as an AE.

The Investigator will evaluate all AEs as to:

- Seriousness: See definition in Appendix 3
- Severity: See definition in Appendix 3.
- Causal Relationship to study drug: See definition in Appendix 3.
- Outcome.

All AEs, serious and non-serious, must be recorded in the AE section of the CRF. SAEs must also be reported to the Sponsor in 24 hours through the SAE form.

After the end of study period, including follow-ups, only if a SAE is believed to be related to the study drug administration should it be reported to the Sponsor.

Adverse Events causing treatment discontinuation

If a subject is withdrawn from the study as a consequence of an AE, this must be recorded and reasoned in the CRF, and the subject must be followed up until the AE outcome resolution.

8.3.5. Prompt Reporting of SAEs to Sponsor

Once an Investigator becomes aware that an SAE has occurred in a study subject, he/she will immediately (within 24 hours from being aware of an SAE) notify the Sponsor:

- by phone ([contact])
- or by e-mail ([contact]) to notify and transmit SAEs.

In case of Serious Adverse Events, the Investigator will transmit electronically if applicable or fill in an SAE form and will transmit it within 24 hours since becoming aware of the event, to Sponsor.

The SAE form must be completed as thoroughly as possible with all details available at that time point and signed by the Investigator (or appropriately qualified designee).

If the Investigator does not have all information regarding an SAE he/she will not wait to receive additional information before notifying the Sponsor of the event and completing the form. The form will be updated when additional information is received (follow up reports).

The Investigator will always provide an assessment of causality at the time of the initial report.

If follow up data obtained after having already reported an SAE indicates that the assessment of causality is incorrect, then a follow up SAE form will be filled in with the amended information, signed and dated, and resubmitted to the Sponsor.

In accordance with local Independent Ethics Committee (IEC) requirements, the Investigator must also notify IEC of any SAEs according the guidelines of the Ethics Committee.

The Investigator, and others responsible for subject care, should institute any supplementary investigations of SAEs based on their clinical judgement of the likely causative factors. This may include seeking further opinion from a specialist in the field of the AE. The Sponsor may also request extra tests. If a subject dies, any post-mortem findings, including histopathology will be provided to the Sponsor if available. No medical help, diagnosis, or advice should be withheld from the subject due to an inability to contact the Sponsor

8.3.6. Follow-up of AEs and SAEs

After the initial AE/SAE report, the investigator is required to proactively follow each participant at subsequent visits/contacts, in order to collect all relevant information. Particularly, all SAEs will be followed until resolution, stabilization, further investigation results are obtained, or the participant is lost to follow-up. Further information on follow-up procedures is given in Appendix 3.

8.3.7. Expeditable Events

Expeditable events are those AEs that are causally related to the study product, and that are both serious and unexpected (Serious Unexpected Suspected Adverse Reaction- SUSAR), see Appendix 3.

8.3.8. Pregnancy

Any pregnancy where the fetus may have been exposed to study drug, should be notified by the Investigator to the Sponsor, by filling in the "Pregnancy Form" and sending it, within 24 hours of its knowledge, to the Sponsor:

- by e-mail ([contact])
- Outcome of the pregnancy (normal or abnormal) must be followed up and recorded.
- Abnormal pregnancy outcome must be notified on an expedited basis (i.e. within 24 hours of the Investigator becoming aware of the abnormal pregnancy outcome) using the SAE form. This refers especially to congenital anomalies in the fetus/child, fetal death and spontaneous abortion, and adverse reactions in the neonate that are classified as serious.
- Pregnancy will be recorded as an AE in all cases. It will be qualified as an SAE only if it fulfils SAE criteria (see above).

8.3.9. Disease Related Events and/or Disease Related Outcomes not Qualifying as AEs or SAEs

Not applicable

8.4. Treatment of Overdose

The investigator should consult the product label of the licensed study medication for advice on treatment of overdose.

8.5. Pharmacokinetics

Pharmacokinetic parameters are not evaluated in this study.

8.6. Pharmacodynamics

Pharmacodynamic parameters are not evaluated in this study.

8.7. Genetics

Genetics are not evaluated in this study.

8.8. Biomarkers

Biomarkers are not evaluated in this study.

8.9. Medical Resource Utilization and Health Economics

Medical Resource Utilization and Health Economics parameters are not evaluated in this study.

9. Statistical Considerations

9.1. Statistical Hypotheses

The superiority of the LABD(s)+ICS group vs. LABD(s) group in terms of time to first re-hospitalization and/or death will be tested. The following hypotheses scheme will be considered:

H_0 : there is no difference in the time to first re-hospitalization and/or death between the two treatment groups.

H_1 : there is a difference in the time to first re-hospitalization and/or death between the two treatment groups

9.2. Sample Size Determination

The sample size calculation is based on the superiority criteria of the LABD+ICS group vs. LABD alone group in terms of re-hospitalization and/or death. With 464 patients in each group, the percentage of patients experiencing the composite event (re-hospitalization and/or death) is expected to be 9% in the LABD+ICS group and 15% in the LABD alone group. A log-rank test (two-sided 5% significance level) will have 80% power to detect a difference between treatment groups in terms of time to first re-hospitalization and/or death (primary efficacy endpoint). Adjusting for an expected 10% dropout rate, a total of 516 patients per group will need to be randomized.

9.3. Populations for Analyses

The following populations will be considered for the analysis:

- **Randomized population:** all randomized patients.
- **Safety population:** all randomized patients who receive at least one administration of the study treatment in a given treatment period.
- **Intention-to-Treat population (ITT):** all randomized patients from the safety population with at least one available post-baseline efficacy evaluation during the treatment period.
- **Per-protocol population (PP):** all randomized patients from the ITT population without any major protocol deviations (e.g., wrong inclusions, forbidden concomitant medications, etc.). The exact definition of major protocol deviations will be discussed with the clinical team case by case during the review of the data and will be described in the Data Review Report.

The statistical analysis will be performed after database lock.

The primary efficacy variable will be analysed both in the ITT and in the PP populations. As this is a superiority study, the primary analysis population will be the ITT. All the other efficacy variables will be analysed in the ITT population only.

Analysis of safety variables will be performed on the safety population.

9.4. Statistical Analyses

All statistical analyses will be undertaken by CROS NT S.r.l. (Verona, Italy) using SAS software, release 9.4 or higher (SAS Institute, Cary, NC, USA).

The following describes the statistical analysis as it is foreseen at the time of planning the trial.

A detailed Statistical Analysis Plan (SAP) will be described in a separate document to be completed after the protocol is finalised and before database lock.

9.4.1. Descriptive Statistics

Descriptive statistics will be provided in summary tables by treatment group according to the type of variable summarized:

- Quantitative variables will be summarized using n (sample size), arithmetic mean, standard deviation (SD), median, minimum and maximum;
- Categorical variables will be summarized using frequency count and percent distribution.

9.4.2. Participant Accountability

Disposition of patients, patient status and patients excluded from analysis sets will be summarized by treatment group.

9.4.3. Description of Baseline Characteristics

The baseline demographic characteristics will be summarized by treatment group by means of descriptive statistics for the ITT population.

The following parameters will be presented:

- demographics;
- medical history (including CV diseases);
- previous and concomitant medications (including CV medications);
- physical examination;
- vital signs;
- efficacy parameters.

9.4.4. Missing Data

The number of patients with missing data will be presented under the “Missing” category, if present. Missing values will be included in the denominator count when computing percentages. When continuous data are being summarized, only the non-missing values will be evaluated for computing summary statistics. Further details on dealing with missing data, along with the handling of possible outliers, will be described in the SAP.

Other critical missing data will be discussed prior to database lock, if any. Decisions will be taken during the data review of the data and will be fully documented in the Data Review Report

9.4.5. Principles of Statistical Analysis

For all inferential analyses, p-values will be rounded to three decimal places. Statistical significance will be declared if the rounded p-value is ≤ 0.05 . No adjustment for multiple testing is planned.

9.4.6. Efficacy Analyses

Primary Efficacy Variable

The primary efficacy variable is the time from baseline (Visit 2) to first re-hospitalization and/or death. If the patient discontinues/completes the treatment period and no re-hospitalization and/or death is observed, then the time to first re-hospitalization and/or death is treated as right censored at the end of treatment period (i.e. date of Visit 6) or at the time of the withdrawal during the treatment period (i.e. the date of discontinuation).

The primary efficacy variable will be analyzed using the Kaplan-Meier estimator. Comparison between treatment groups will be performed using the log-rank test stratified by center. A Kaplan-Meier plot for time to first re-hospitalization and/or death will also be presented by treatment group.

The LABD(s)+ICS group will be declared to prolong time to first re-hospitalization and/or death, compared to the LABD(s) group, if the difference between the two treatments is significantly in favour of LABD(s)+ICS (i.e. the p-value from the log-rank test is ≤ 0.050).

In addition, a Cox proportional hazards regression analysis will be performed as well, presenting the treatment effect as a hazard ratio with the associated 95% confidence interval with center, age and treatment group as factors. The inclusion of any other potential confounding factors in the model will be evaluated during the Data Review, verifying the homogeneity of factors distributions among treatment groups.

A sensitivity analysis will be also carried out excluding efficacy data (i.e. hospitalization and death) collected after the crossover occurrence (i.e. patients that switch from one treatment group to the other adding or stopping ICS). The crossover patients that do not experience any hospitalization or death will be considered as censored at the time of cross-over start. Kaplan-Meier, log-rank test and Cox model will be repeated on this modified analysis dataset.

Secondary Efficacy Variables

The number of re-hospitalizations and deaths (all cause) will be analysed using a Poisson regression model. The model will include the number of events as dependent variable and treatment group, age and center as factors. Log-time on study will be used as an offset. The over dispersion parameter based on the deviance will be considered in order to account for between-patient variability in the events rate and standard errors will be estimated allowing for extra-Poisson variation.

All the other counting variables will be analysed with the same model.

All the continuous variables will be summarized at each visit by means of descriptive statistics. Mean change from baseline value and the 95% confidence intervals will be calculated. P-values of paired t-tests will be provided for mean changes from baseline.

Change in continuous variables will also be analysed using an ANCOVA model, with treatment group, centre and age as factors and baseline as covariate.

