1.2. Schema

1.3. Schedule of Activities (SoA)

Procedure	Screening (up to 10 days before Day 1)	Intervention Period [months]					Follow-up (3 months after last study treatment)	Notes
		day 1 (randomiz ation)	3 months	6 months	9 months	12 months (or early withdrawal)		
Visit number	Visit 1	Visit 2	Visit 3	Visit 4	Visit 5	Visit 6	Visit 7	
Informed consent	X							
Inclusion and exclusion criteria	X	X						Recheck clinical status before randomization and/or 1 st dose of study medication.
Spirometry*		X				X		Participant must have a diagnosis of COPD confirmed by spirometry (performed within the last 3 years) prior to randomization.
COPD assessment test (CAT)	X	X	X	X	X	X	X	
mMRC dyspnea scale	X	X	X	X	X	X	X	
Demography	X							
Physical examination including height and weight	X	X	X	X	X	X	X	
Medical history (including substance usage (review and update after screening if necessary)*	X	X	X	X	X	X	X	Substances: alcohol, tobacco, and caffeine Medical history will be reviewed and updated at the follow-up visits

Procedure	Screening (up to 10 days before Day 1)	Intervention Period [months]					Follow-up (3 months after last study treatment)	Notes
		day 1 (randomiz- ation)	3 months	6 months	9 months	12 months (or early withdrawal)		
Visit number	Visit 1	Visit 2	Visit 3	Visit 4	Visit 5	Visit 6	Visit 7	
History of COPD and cardiovascular disease (particularly HF, IHD or AF)	X	X	X	X	X	X	X	Participants must have concomitant CV disease (HF, IHD or AF) and must be receiving treatment (see Appendix 10.5) to be eligible for the study
Past and current medical conditions	X							Participants must have at least one concomitant major CV condition (HF, IHD or AF)
Laboratory assessments	X							
12-lead ECG	X					X		For stable patients a previous ECG recording (within the last 3 months) can be used
Chest x-ray	X (Optional)							Chest x-ray data will be collected if available
Vital signs (blood pressure and heart rate)	X	X	X	X	X	X		
Randomization		X						
Study treatment checked and prescribed		X	X	X	X			
Assessment of symptoms and hospitalizations			X	X	X	X	X	Also assessed via monthly telephone contact between visits

Procedure	Screening (up to 10 days before Day 1)	Intervention Period [months]					Follow-up (3 months after last study treatment)	Notes
		day 1 (randomiz- ation)	3 months	6 months	9 months	12 months (or early withdrawal)		
Visit number	Visit 1	Visit 2	Visit 3	Visit 4	Visit 5	Visit 6	Visit 7	

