7.1. Discontinuation of Study Intervention

Participants who are hospitalized during the study period will be allowed to continue in the study until the end at the discretion of the principal investigator and/or the participant. The investigator/participant can decide to discontinue the study drug for safety or efficacy reasons.

Albeit we will invite patients and doctors to stick to the initial treatment unless required by changed medical condition, the specific COPD treatment regimen (LABD(s) without ICS or LABD(s) + ICS) can be changed at any point during the study. Treatment with ICS in the only LABDs group will be permitted if, on clinical Investigators judgement, it would be necessary for patient temporary conditions for at maximum 15 days in case of patient treated at home or for 15 days (at maximum) after hospital discharge in case of hospitalised patient. If the ICS treatment will surpass these periods, the patient will be considered being switched to the LABD + ICS group and considered as protocol violator.

See the SoA for data to be collected at the time of intervention discontinuation and follow-up and for any further evaluations that need to be completed.

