7.3. Lost to Follow Up

A participant will be considered lost to follow-up if he or she repeatedly fails to return for scheduled visits and is unable to be contacted by the study site.

The following actions must be taken if a participant fails to return to the clinic for a required study visit:

- The site must attempt to contact the participant and reschedule the missed visit as soon as possible and counsel the participant on the importance of maintaining the assigned visit schedule and ascertain whether or not the participant wishes to and/or should continue in the study.
- Before a participant is deemed lost to follow up, the investigator or designee must make every effort to regain contact with the participant (where possible, 3 telephone calls and, if necessary, a certified letter to the participant's last known mailing address or local

equivalent methods). These contact attempts should be documented in the participant's medical record.

- Should the participant continue to be unreachable, he/she will be considered to have withdrawn from the study.

8. Study Assessments and Procedures

- Study procedures and their timing are summarized in the SoA. Protocol waivers or exemptions are not allowed.
- Immediate safety concerns should be discussed with the sponsor immediately upon occurrence or awareness, to determine if the participant should continue or discontinue study intervention.
- Adherence to the study design requirements, including those specified in the SoA, is essential and required for study conduct.
- All screening evaluations must be completed and reviewed to confirm that potential participants meet all eligibility criteria. The investigator will maintain a screening log to record details of all participants screened and to confirm eligibility or record reasons for screening failure, as applicable.
- Procedures conducted as part of the participant's routine clinical management (such as spirometry, ECG and chest x-ray) and obtained before signing of the ICF may be utilized for screening or baseline purposes provided the procedures meet the protocol-specified criteria and were performed within the time frame defined in the SoA.

Identification of suitable participants

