The participant's ongoing treatments (concomitant medications including any anti-influenza and anti-pneumococci vaccinations) will be reviewed and updated as necessary both for COPD and CV comorbidities, particularly HF, IHD and/or AF. Details of all concomitant medications will be recorded. Doses of all COPD medications can be adjusted by the clinical investigator according to licenced dosages for COPD for each inhaled drug, at any time during the study.

Participants will be questioned about the occurrence of any adverse events and details will be recorded on the eCRF.

Prescriptions for further supplies of the study medication, for collection from the local pharmacy or hospital pharmacy department, will be issued. Prescription data will be captured on the eCRF.

Visit 6: End of Study after 12 months of treatment or early withdrawal

Participants will be asked to complete the CAT and mMRC questionnaires.

Spirometry will be performed in accordance with ATS and ERS guidelines (Miller et al 2005). The spirometry test will be performed before and 30 minutes after bronchodilation (4 inhalations of 100 µg salbutamol).

Vital signs, including blood pressure and heart rate, will be measured. A 12-lead ECG will also be performed.

Medical history and history of COPD and CV disease will be reviewed and updated as necessary.

Participants will be asked to bring back all the unused medication and the empty drug devices and they will also be asked about their compliance with the study procedures and treatment.

Information about any hospitalizations or any unexpected medical events, particularly moderate exacerbations treated with antibiotics and/or steroids will be collected. Information will be obtained by reviewing the patient's medical records and prescribed medication and also from direct questioning of the participant.

Participants will be questioned about the occurrence of any adverse events and details will be recorded on the eCRF.

For participants who are withdrawn before the end of the study the reason for early withdrawal will be recorded on the eCRF.

Participants who complete the 12 month randomized treatment period will continue to be prescribed the most appropriate treatment for their condition at the discretion of the investigator. Doses of all COPD medications can be adjusted by the clinical investigator according to licenced dosages for COPD for each inhaled drug, at any time during the study.

Visit 7: Follow-up 3 months after End of Study

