7.1 Analysis of primary endpoint

Definitions and data conventions

First re-hospitalization and/or death

The event “first re-hospitalization and/or death” is identified as the first occurrence between the first re-hospitalization (as collected in the “COPD EXACERBATION FORM”) and death, if any of them occurred.

Time to first re-hospitalization and/or death

Forms			
Title		Statistical Analysis Plan Template	
Code		Version	Effective Date
FRM_ST03_032		02	02 Oct 2017
			17 of 26

In patients with at least one event, time to first re-hospitalization and/or death will be calculated as the weeks between baseline (Visit 2) and the date at which the first re-hospitalization (i.e., Date of admission/prolonged hospitalization in the ‘COPD Exacerbation Form’) and/or death occurs.

Time to first re-hospitalization and/or death (weeks) = (date of first re-hospitalization and/or death - Visit 2 + 1)/7

Patients without first re-hospitalization and/or death or who are discontinued before having it will be considered as “censored” at the end of the study visit (Visit 6) or at the time of the withdrawal during the treatment period (i.e., the date of withdrawal). For the analysis, the following formula will be applied:

Censoring time (weeks) = (date of Visit 6/withdrawal - Visit 2 + 1)/7

Time to first re-hospitalization and/or death for the sensitivity analysis.

The crossover occurrence is identified as patients that switch from one treatment group to the other adding or stopping ICS and it will be identified as protocol deviation.

In patients without the crossover occurrence , time to first re-hospitalization and/or death will be calculated as described above.

In patients with the crossover occurrence:

- if they experienced first re-hospitalization and/or death before or at the crossover occurrence date, time to first re-hospitalization and/or death will be calculated and considered as for the patients without the crossover occurrence;
- if they experienced first re-hospitalization and/or death after the crossover occurrence date, time to first re-hospitalization and/or death will be censored at the time of crossover occurrence;
- patients without first re-hospitalization and/or death will be considered as “censored” at the cross-over start date. For the analysis, the following formula will be applied:

Censoring time (weeks) = (date of cross-over start - Visit 2 + 1)/7

Primary efficacy analysis

Analysis will be performed on ITT population.

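### First events after early discontinuation or withdrawal are left out of the primary ITT analysis, and follow-up to month 12 is not required for these patients

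*Protocol*

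**What the plan says.** **Censoring.** Protocol 9.4.6 applies to a patient who discontinues or completes the treatment period without an event. Censoring is at Visit 6 or "at the time of the withdrawal during the treatment period (i.e. the date of discontinuation"). SAP 7.1 carries this over: "Patients without first re-hospitalization and/or death or who are discontinued before having it will be considered as" censored at Visit 6 or at the withdrawal date. SAP 5.3 takes the discontinuation date from the study conclusion/withdrawal form.

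**Stopping treatment.** Protocol 7.1 states: "The investigator/participant can decide to discontinue the study drug for safety or efficacy reasons". For data collection after stopping, 7.1 and 7.2 both refer to the Schedule of Activities (SoA).

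**Visits.** The SoA has one column for the 12-month visit or early withdrawal, and Protocol section 8 names it "Visit 6: End of Study after 12 months of treatment or early withdrawal". The last column is "Follow-up (3 months after last study treatment"), so Visit 7 is timed from treatment and not from randomisation. Hospitalizations are still recorded at Visit 7.

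**Regimen switches.** Under Protocol 9.4.6 and SAP 7.1, events after a patient adds or stops ICS are removed only in the crossover sensitivity analysis. The primary analysis counts them.

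**Adverse events.** SAP 8.1 classes an adverse event as leading to study withdrawal when the action taken was that the drug was withdrawn or interrupted.

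**Unreachable patients.** Protocol 7.3: "Should the participant continue to be unreachable, he/she will be considered to have withdrawn from the study".

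**The concern.** An intention-to-treat comparison of two strategies over a year needs each patient's first event in that year, whatever happened to treatment. Here the clock can stop early. Take a patient withdrawn at month 3. Visit 6 moves to month 3 and Visit 7 falls at about month 6. An admission at month 5 is recorded but lies after the censoring date, and nothing requires months 6 to 12 to be observed.

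The log-rank test and the Cox model both assume that censoring carries no information about risk. The trial is open-label and treatment may be stopped for safety or efficacy reasons, so stopping is plausibly related to prognosis and may differ by arm. The plan is also uneven: events after a regimen switch count, while events after discontinuation do not. The only sensitivity analysis censors more patients, so it cannot show what the discontinuation rule does.

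**Working it through.** **1. The plan's own figure.** Protocol 9.2 gives event rates "expected to be 9% in the LABD+ICS group and 15% in the LABD alone group", 80% power and a two-sided 5% level.
- Hazard ratio: ln(0.91)/ln(0.85) = 0.0943/0.1625 = 0.580.
- Freedman events: (1.960 + 0.842)² × [(1 + 0.580)/(1 − 0.580)]² = 111.3.
- Per group: 111.3/(0.09 + 0.15) = 463.7, so 464.
- With 10% dropout: 464/0.90 = 515.6, so 516.

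The sample size reproduces and is not in question.

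**2. Model for uncounted events.** From the documents: the 12-month risks of 15% and 9%, and 516 per group. Assumed, because the documents give neither: a proportion d stops over the year at a constant rate, and the hazard after stopping is k times that arm's own hazard. The value d = 10% borrows the dropout figure, which is not a stated rate of stopping treatment.

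With h the arm's hazard, s = −ln(1 − d), a = h + s, and time in years:
- counted = 516 × (h/a)(1 − e^(−a))
- uncounted = 516 × ∫₀¹ s·e^(−at)·[1 − e^(−kh(1−t))] dt

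At d = 10%, s = 0.1054.
- LABD: a = 0.2679; counted = 516 × 0.6067 × 0.2350 = 73.6.
- LABD+ICS: a = 0.1997; counted = 516 × 0.4723 × 0.1810 = 44.1.
- Total counted: about 118.

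**3. Results.** The full hazard ratio is the ratio of events per person-time to month 12, with all first events counted. The censored value is 0.580 in every row.

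| Stopping, LABD / LABD+ICS | k | Uncounted events, LABD / LABD+ICS | Share of the arm's first events | Full 12-month HR |
|---|---|---|---|---|
| 10% / 10% | 1 | 3.8 / 2.3 | 5% / 5% | 0.580 |
| 10% / 10% | 3 | 10.4 / 6.6 | 12.3% / 12.9% | 0.583 |
| 15% / 5% | 3 | 15.7 / 3.3 | 18% / 7% | 0.535 |
| 5% / 15% | 3 | 5.1 / 9.9 | 6% / 19% | 0.635 |

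With balanced 10% stopping, the uncounted total runs from about 6 (k = 1) to about 17 (k = 3).

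**4. A different assumption after stopping.** Suppose both arms move to k times the LABD hazard, so that any ICS benefit ends on stopping. With balanced 10% stopping, about 8 (k = 1) to 21 (k = 3) events are uncounted, which is 6% to 15% of all first events. The full hazard ratio is then 0.60 to 0.63. So the finding that balanced stopping leaves the hazard ratio unchanged depends on the multiplier in step 2 acting alike in both arms.

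**The case against.** A reader might infer that the primary result is an on-treatment comparison, or that anyone who stops study drug is closed out. The documents do not support either reading.

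- Protocol 7.1 (stopping the intervention) and 7.2 (leaving the study) are separate sections. Section 7.1 lets hospitalised patients continue to the end and lets the regimen change at any point.
- The SAP takes the discontinuation date from a study-exit form, not from the last dose. The tie to last study treatment schedules Visit 7 only.
- Patients who add or stop ICS and remain in the study, plausibly the commonest departure in a trial of licensed inhalers, keep counting in the primary analysis.

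This limits the point to patients who discontinue the treatment period or are withdrawn. Within that group the gap remains. No section requires event collection to month 12, and SAP 8.1 blurs stopping drug with leaving the study.

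A second inference would be that deaths among unreachable patients are simply missed. Protocol 7.3 lists only attempts to reach the participant or equivalent local methods. However, 8.1.1 collects deaths from medical records, so a missed death is possible but not built into the plan.

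The size is also open to challenge. The documents give no stopping rate by arm and no hazard after stopping. Under the same-multiplier model, balanced stopping produces almost no bias.

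**Conclusion.** The point holds for patients who discontinue the treatment period or are withdrawn early. Their later first events within 12 months of Visit 2, including those already recorded at Visit 7, do not enter the primary analysis, and no planned analysis tests that choice.

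With an assumed 10% stopping and a hazard one to three times as high afterwards, about 5% to 13% of first events are lost. The effect on the hazard ratio may be negligible. It becomes material if stopping differs by arm and carries risk, and its direction then depends on which arm stops more. It can also move with balanced stopping if the arms' hazards converge afterwards. These sizes rest on assumed rates, and sites may in practice have followed such patients longer than the plan requires. This should be fixed because it concerns the primary estimate and costs little. It does not invalidate the sample size or the analysis as a whole.

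**What to change.** - **Protocol 7.1, 7.2 and SoA:** state that patients who stop study treatment without withdrawing consent continue the existing monthly calls and visits to 12 months from Visit 2.
- **Protocol 9.4.6 and SAP 7.1:** count every first re-hospitalization or death up to 12 months from Visit 2 whatever the treatment status, including events recorded at Visit 7. Censor only at month 12, withdrawal of consent or last contact.
- **Data capture and SAP 5.3 and 8.1:** record treatment stop and study withdrawal as separate dates, and stop labelling a drug interruption as study withdrawal.
- **Protocol 7.3:** check medical records, already the source for deaths in 8.1.1, before coding an unreachable patient as an event-free withdrawal.
- **Sensitivity analysis:** keep the present censoring rule in this role.

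The cost is a protocol clarification, SAP wording and the remaining calls for about 10% of patients. The estimate will include events after stopping, which is what ITT implies. If follow-up is already complete, the SAP change alone still recovers events recorded at Visit 7. The planned 464 and 516 per group stand.
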